9.3. Planned Interim Analyses (If Applicable)

We will review safety data (adverse events) continuously, however, no formal interim analyses are planned.

9.4. Plans for Coping with Withdrawals and Loss-To-Follow-Up

Enrolled participants who discontinue treatment/or withdrawn from study will not be replaced. Allowing for a 20% drop out rate, approximately 55 - 60 subjects will be enrolled.

9.5. Sample Size Rationale

Tolerability: The sample size for tolerability was not determined from power analysis but based on multiple previous clinical trials conducted with GOS⁵⁸⁻⁶¹.

Microbiome: Our previous studies^{10, 11, 31, 32} conducted with a different but equivalent GOS preparation (purified prebiotics) have demonstrated a consistent and statistically significant increased abundance of the targeted beneficial bacteria: *Bifidobacterium* and *Akkermansia*. The proposed pilot study will recruit

60 subjects. After estimated dropout rate of 20%, the final subjects that will complete the subject will be N=48, which is 16 for each arm. This sample size is chosen given limited funds available with the pilot award supporting this project.

Biomarkers of inflammation: Since this is the first study, we do not have the estimate of effect size so the power cannot be computed. Additionally, due to the limitation of the funding with n=20, we do not expect to have sufficient power to detect differences over time. In that case, we will perform an exploratory analysis of changes in plasma cytokines and biomarkers of inflammation and compare the summary statistics such as mean and standard error.

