Target Population	
Healthy adult individuals
 
Key Inclusion Criteria: Individuals ages 18-55 with BMI of 18.5 to 32.
 
Key Exclusion Criteria:
 
 Formal diagnosis of IBD (including ulcerative colitis, Crohn's Disease) colorectal cancer, diabetes Celiac disease or IBS diagnosed by a physician Lactose intolerance as diagnosed by a hydrogen breath test C. difficile infection within 2 months Antibiotic consumption in the previous 2 months History of gastric bypass surgery Current tobacco smoker Pregnant or breastfeeding A response of 4 or 5 to questions 2 (abdominal pain), 6 (abdominal discomfort), 8 (constipation), 16 (diarrhea), 22 (abdominal distention), 26 (abdominal bloating), 31 (nausea), or 33 (vomiting).
Numbers of Participants	
Number to be recruited for screening: 55-60 participants
 
Number of eligible participants enrolled: 48 adult individuals

Clinical Phase	Pilot
Intervention	Daily oral administration of 10 - 15 g of Prebiotic galacto-oligosaccharides (GOS) or GOS enriched with lactosamine (LacNAc) for four weeks
Study Description	We will enroll 48 adult individuals (18-55 y.o.). Subjects will be assigned randomly to one of 3 groups (n = 16): GOS, hGOS or placebo (powdered corn syrup comprised of fructose, glucose, and an inert cellulose material that matched the consistency, color, sweetness, and taste of the prebiotics) to test safety and dose tolerability. The prebiotic treatment will last for 4 wk. Before the treatment (baseline) and during week 4 of the trial (after the prebiotic treatments), we will assess changes in quality and quantity in bacterial components of the gut microbiome pre- and post-treatment. Likewise, we will

	determine serum markers of inflammation, integrity of the intestinal barrier at baseline and at week 4. Participants will complete the Diet History Questionnaire (DHQ), a freely available food frequency questionnaire (FFQ) at baseline and will be asked to maintain a record of their daily diet by using a printed meal tracking diary. In addition, the PROMIS Gastrointestinal Symptom Scale will be used for potential side effect evaluation at baseline and each week for the duration of the study.
Outcome Measures	Dose safety and tolerability in healthy adults . Gut microbiome Inflammation Integrity of intestinal barrier
Study Duration	4 weeks
Subject Participation Duration	4-5 weeks
Estimated Time to Complete Enrollment	40 weeks

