Before the treatment (baseline) and during week 4 of the trial (after the prebiotic treatment), we will assess changes in quality and quantity in bacterial components of the gut microbiome pre- and post-treatment. Likewise, we will determine serum inflammatory markers, and integrity of the intestinal barrier at baseline and at week 4. Subjects will also respond to the Diet History Questionnaire (DHQ), a freely available food frequency questionnaire (FFQ) and will be asked to keep daily diet records.

3. Objectives

3.1. Specific Aim 1

To validate 15 g/day dose safety and tolerability of GOS and hGOS in **healthy adults**.

3.2. Specific Aim 2

To establish a biological signature of GOS and hGOS through assessment of prebiotics effects vs placebo on (i) abundance of beneficial gut bacteria and restoration of the gut microbiome saccharolytic potential, (ii) modulation of biomarkers of inflammation and (iii) evaluation of intestinal barrier function.

4. Study Design

[figure not shown]
This will be a controlled (GOS, hGOS versus placebo), interventional, longitudinal (baseline compared to end of study), prospective, single-site pilot study. Subjects will be assigned randomly to one of 3 groups (n = 16): GOS, hGOS or placebo. The treatment will consist in 10 - 15 g/day of GOS, hGOS or placebo (powdered corn syrup comprised of fructose, glucose, and an inert cellulose material that matched the consistency, color, sweetness, and taste of the prebiotics), which will be provided to participants as powder that can be added to any non-alcoholic beverage or sprinkled on food for intake. The intervention will last for 4 weeks, since we have shown in adult individuals that a 4 week period allows for the observation of changes to the gut microbiome. The study will end after the second time-point sample collection at 4 weeks.

Dose rationale: The intervention will include a dose of 5 grams twice daily on days 1–10 followed by 7.5 grams twice daily on days 11–28¹⁰. Doses were selected based on previous literature reports^{16, 17, 28-30} and the interventions conducted by our group to assess efficacy of GOS in lactose-intolerant individuals^{10, 11, 31, 32}. The hGOS preparation will be composed of GOS enriched with LacNac at a concentration of 6.7–31µg/mL (<1% of the formulation), which is in the range found in human breast milk³³ and hence considered safe.

Flow diagram

Prior to Enrollment

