5.1. Number of Participants

Number to be recruited for screening: 55-60 participants will be recruited for screening.

Number of eligible participants enrolled: The targeted number of participants is 48. We expect that 20% of screened individuals will not be eligible or will be unwilling/unable to participate in the study. Participants will be adults (male and female, 18-55 years old with no formal diagnosis of IBD, IBS, UC, CRC, celiac disease, or diabetes mellitus) recruited at UNC Chapel Hill and within the general population in the surrounding area via email communications, social media, and flyers.

Subjects will not be diagnosed with specific GI conditions (IBD, IBS, UC, CRC) and with no history of celiac disease, diabetes mellitus or antibiotic consumption in the previous 2 months. Individuals with a non-GI related disease diagnosis might be included in the study.

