5.3. Strategies for Recruitment and Retention

Recruitment Strategy:

Subjects will be recruited using study flyers and/or asked to participate in the study via email or phone call. Only if the subject agrees to participate and meets enrollment criteria will they be enrolled in the study. Subjects will be screened by the Clinical Research Coordinator on the basis of inclusion and exclusion criteria laid out in this study. Only individuals with no formal diagnosis of IBD, IBS, UC, CRC, celiac disease, or diabetes mellitus will be selected as study participants based on a self-report. Also, individuals with a history of gastric bypass, current use of antibiotics or use of oral antimicrobials in the past 2 months will be excluded. The PI will review subject enrollment at weekly project meetings so that any deviation from the anticipated enrollment schedule will be detected quickly. All outreach and advertising activities will also be reviewed on a weekly basis.

Retention Strategy:

The PI and research team will hold weekly project meetings to monitor enrollment and ensure enrolled subjects complete all study procedures as intended. Likewise, brief weekly contacts (either by phone, email, or text message) with enrolled subjects will follow up regarding protocol adherence, gastrointestinal symptoms, and study satisfaction, in addition to any protocol-specific procedures. This approach provides the opportunity for early identification of possible reasons for study non-adherence or early discontinuation by the subject and to address such issues, if possible. If a subject decides to withdraw participation in the study, the date and reason will be recorded and stored in the RedCap database. On a weekly basis, the study coordinator will run a report on participants accrual and completion status for review by team to identify and resolve any problems or potential issues that arise during the course of the study.

Screen Failures:

During the screening period, inclusion/exclusion criteria for the study participation will be checked / tested. Subjects who meet all inclusion criteria and do not meet any exclusion criterion will be eligible to be randomized. Those who are not eligible for randomization or dosing will be considered as screening failures. In the case of screen failures, the reason will be recorded. We expect a 20% screen failure rate.

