8.6. Variables Representing Treatment

A total of 45 individuals will be randomized 1:1:1 (placebo, GOS, hGOS) to treatment. Allowing for a 20% drop out rate, approximately 55 - 60 subjects will be enrolled.

9. Statistical Analysis Plans

a. Strategies that Apply to all the Specific Aims

- (1) To help ensure replicability of the research, the analysis plans will be reviewed and finalized prior to collection of data (a priori). For the specific aim, the analysis plan specifies detailed steps for obtaining estimates of population parameters (e.g intervention safety) and for making inferences.
- (2) Sensitivity analyses will be performed to assess the robustness of the major results as indicated by their sensitivity to reasonable perturbations of the choices of the methods and assumptions used. Any question about the optimal choice of methods and assumptions are best handled by relegating competing approaches to roles in the domain of sensitivity analyses. Results of the sensitivity analyses will be used to guide our level of trust in the main results. Best practices for dealing with incomplete data will depend on the documented causes of missing, censored, and coarsened values. The reasons for missing data values, drop-out, and protocol departures will have been documented in/with the database.
- (3) The plan also includes outcome-dependent exploratory analyses to generate new hypotheses.
- (4) Descriptive graphical and tabular methods will be used to characterize the participants, visualize the data, and examine relationships among variables.
- (5) To indicate precision, all statistical estimates of population parameters will be tabulated along with corresponding confidence intervals (CI) or standard errors (SE). The CI will be interpreted as the set of potential values of the population parameter that are most compatible with the observed data.
- (6) All hypothesis tests yielding p-values that are deemed to be not statistically significant will be reported as being inconclusive. The proposed statistical analysis strategy acknowledges that no p-value can reveal the plausibility, presence, truth, or importance of an association or effect-- which is consistent with the statements of the American Statistical Association [4,5], the recommendations in Nature [6,7], and guidance, such as the CONSORT Statement [1], STROBE Statement [2], and ICMJE guidance [3].²

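### The figure of 48 (16 per arm) is used both as the number enrolled and assigned and as the number completing; if 48 are randomised, the plan's own 20% drop-out leaves about 38 completers for Aim 2

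*Combined protocol and SAP*

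**What the plan says.** **Enrolled and assigned.** The synopsis states "Number of eligible participants enrolled: 48 adult individuals". Section 5.1, under its heading for eligible participants enrolled, says "The targeted number of participants is 48". Section 2.3 says "Subjects will be assigned randomly to one of 3 groups (n = 16): GOS, hGOS or placebo"; the synopsis and sections 4 and 4.2 also assign 16 per group, and the flow diagram in section 4 shows a total of 48 after consent and screening.

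**Screened.** The synopsis gives "Number to be recruited for screening: 55-60 participants", and 5.1 repeats the range. Section 5.1 adds "We expect that 20% of screened individuals will not be eligible or will be unwilling/unable to participate in the study", and 5.3 says "We expect a 20% screen failure rate".

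**Completing.** Section 9.5 recruits 60 and continues: "After estimated dropout rate of 20%, the final subjects that will complete the subject will be N=48, which is 16 for each arm".

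**Other counts.** Section 8.6 says "A total of 45 individuals will be randomized 1:1:1 (placebo, GOS, hGOS) to treatment". Sections 8.6 and 9.4 both then put the number enrolled at about 55–60, as an allowance for 20% drop-out. In its paragraph on inflammation biomarkers, 9.5 mentions n=20 without saying what it counts.

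**Handling of losses.** Section 9.6 expects 20% drop-out during the study and makes complete-case analysis primary. Section 9.4 rules out replacement. Section 7.8 keeps the data of discontinued participants for Objective 1 but not for Objective 2.

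**The concern.** The same step from 60 to 48 does two jobs. In 5.1 it is the loss between screening and enrolment; in 9.5 it is the loss between recruitment and completion. These are different losses at different times, and the plan expects each to be 20%. If the first takes 60 down to 48, the second still has to be taken from 48.

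Two things are at stake. First, the site needs one number to randomise, because the allocation list, product supply and sampling budget all depend on it; the text gives 48 in most places and 45 in one. Second, 9.5 promises 16 completers per arm for Aim 2. With no replacement, discontinued participants left out of Objective 2 and a complete-case primary analysis, nothing in the plan makes up a shortfall. Multiple imputation in 9.6 is a conditional sensitivity analysis and adds no observed completers. In a pilot whose size 9.5 attributes to limited funds, the head count is the only size commitment made, so it should be unambiguous.

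**Working it through.** **Inputs**
- Screened: 55–60 (synopsis, 5.1)
- Loss at screening: 20% (5.1, 5.3)
- Enrolled and assigned: 48, i.e. 3 × 16 (synopsis, 2.3, 4, 4.2, 5.1)
- Drop-out during the study: 20% (9.6)
- Recruited and completing: 60 and 48 (9.5)
- Randomised: 45 (8.6)

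**1. The plan's own figure.** Completers = N × (1 − drop-out) = 60 × 0.80 = 48, and 48/3 = 16 per arm. This reproduces 9.5 exactly.

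**2. Both stated losses in sequence**
- From 60 screened: 60 × 0.80 = 48 randomised; 48 × 0.80 = 38.4 completers; 38.4/3 = 12.8 per arm.
- From 55 screened: 55 × 0.80 = 44 randomised; 44 × 0.80 = 35.2 completers.

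**3. Spread around 38.4.** With completers distributed as Binomial(48, 0.8), the 2.5th and 97.5th percentiles are 33 and 43. Having all 48 complete has probability 0.8^48 ≈ 0.00002. Relative to the figure in 9.5, the expected shortfall is (48 − 38.4)/48 = 20%.

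**4. What 48 completers would require.** 48/0.80 = 60 randomised, or 20 per arm; 60/0.80 = 75 screened, against 55–60 planned.

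**5. Lower end of the screening range.** At 55 screened, 44 remain after a 20% loss, 4 short of 48. Reaching 48 from 55 allows a loss of only 1 − 48/55 = 12.7%. At 60 the allowance is 1 − 48/60 = 20%, which matches.

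**6. The 45 in 8.6.** If 45 are randomised, 45 × 0.80 = 36 complete (12 per arm). Run the other way, 45/0.80 = 56.25, inside 55–60. So 45 behaves like a number remaining after drop-out, although the text calls it randomised. That is an inference; the documents do not explain it. Likewise n=20 would fit 60/3, but the text does not say so.

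**7. Per-arm figures are averages.** Section 6.2 specifies simple randomisation. If that means independent assignment with probability 1/3, 48 participants split exactly 16/16/16 only about 2% of the time. The 95% range for any one arm is 10–23 randomised and, at 20% drop-out, 7–19 completers.

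**Readings compared**

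| Randomised | Expected completers | Conflicts with |
|---|---|---|
| 48 | 38.4 | 9.5 (48 completing); 8.6 (45) |
| 60 | 48 | synopsis, 2.3, 4, 4.2, 5.1; 8.6 (45); 55–60 screened |
| 45 | 36 | synopsis, 2.3, 4, 4.2, 5.1; 9.5 |

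No single number satisfies every section.

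**The case against.** The strongest reply is that 9.5 is internally correct and this is only a matter of labels. Its first half stands: a reader might infer a miscalculation in 9.5, and the documents do not support that. The error lies in attaching one number to two populations.

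A second reply is that enrolled may be used loosely. Section 7.2 is headed as enrolment and pre-screening, so the 55–60 enrolled in 8.6 and 9.4 might be people entering screening. The term is not defined, so this cannot be excluded. But both sections justify 55–60 by drop-out rather than screen failure, and 5.3 reserves enrolment for those who meet the criteria. The ambiguity also cuts the other way. A reader might take 8.6 and 9.4 to say that 55–60 are randomised; they do not, and 8.6 separately gives 45 as the number randomised.

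A third reply is that little depends on it. Section 9.5 says the tolerability size did not come from a power analysis, attributes the microbiome size to funds and expects low power for the biomarkers. This stands in part: no stated power or success threshold changes. A stated sample size that the design is not expected to deliver still needs correcting.

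On Aim 1 the effect is smaller. Section 9.2 counts adverse events in all individuals, the table of events schedules the symptom scale at premature discontinuation, and 6.8 and 10.2 follow up those who withdraw. Symptom scores after exit can still be missing.

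Finally, 55–60 is a planning range whose upper end gives exactly 48, so the point about 55 is minor.

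**Conclusion.** The concern holds as a conflict of counts and should be fixed. If 48 are randomised, which is what the synopsis and sections 4 and 5.1 indicate, about 38 participants are expected to contribute to Aim 2 (95% range 33–43; about 13 per arm on average), 20% below the figure in 9.5. This rests on four assumptions: 48 is the number randomised; the 20% drop-out in 9.6 applies after randomisation; drop-outs occur independently, for the binomial range; and discontinued participants supply no Objective 2 data, as 7.8 says.

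The 48 completers of 9.5 hold only if 60 are randomised, and no section says that.

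A reader might infer that the trial loses planned power. The documents do not support that: they give no significance level, power, effect size or standard deviation from which a loss could be derived.

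**What to change.** Define screened, randomised and completed once, and use the same chain throughout: 60 screened, 48 randomised (16 per arm on average, given the simple randomisation in 6.2) and about 38 expected completers for Aim 2 (about 13 per arm on average). Then:

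- **9.5:** restate along the lines of: About 38 of the 48 randomised participants, on average about 13 per arm, are expected to contribute to Aim 2; adverse-event summaries include all 48. Remove or explain n=20.
- **8.6 and 9.4:** say that 55–60 (or 60) are screened and 48 randomised. Remove or explain 45.
- **Synopsis and 5.1:** give 60 as the number to screen, or keep 55–60 with a screening loss that fits 55 (about 12.7%).

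This costs wording only. No participant is added, and the stated completer number falls from 48 to about 38.

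If the sponsor does intend 48 completers, the synopsis, 2.3, 4, the flow diagram, 4.2, 5.1, 8.6 and 9.4 must all move to 60 randomised (20 per arm) from about 75 screened. Compared with 48 and 60, that is 12 more randomised and 15 more screened, with their product and sampling, under funding that 9.5 describes as limited. It is not a cheap change and is not the recommended one.

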9.6. Missing data

We expect a 20% drop out during the proposed study. We assume the subjects will drop out randomly and all the missing data is missing completely at random (MCAR). In this case, we will implement complete-case analysis for the primary statistical analysis. However, we will also explore the possibility that the missing data is not MCAR. In the sensitivity analysis, we will compare the drop-out and non-drop group in terms of demographic characteristics and clinical factors. More specifically, we will perform two-group testing between the drop-out and non-drop group using either t-test, Wilcoxon test or chiq-square test depending on distribution and type of the variables of interest. If the missing data is indeed missing at random (MAR), we will perform multiple imputation method to generate the missing values with Rubin's rule to obtain the unbiased inference, which will be compared with results from the primary statistical results.

10. Safety Monitoring and Management

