6.7. Withdrawal / Discontinuation of Enrolled Participants

At baseline and every week after for the duration of the study, participant will answer a 33 question gastrointestinal symptom assessment with the PROMIS Gastrointestinal Symptom Scale (Spiegel, et al, Am J Gastrol, 2014). If a subject experience and increase in 2 levels over baseline in their response to questions 2 (abdominal pain), 6 (abdominal discomfort), 8 (constipation), 16 (diarrhea), 22 (abdominal distention), 26 (abdominal bloating), 31 (nausea), or 33 (vomiting) on the PROMIS Gastrointestinal Symptom Scale, they will be a) withdrawn from the study if the participant is in the first 10 days of their participation, or b) asked to go back to the lower dose of 5g sachets twice daily and reassessed in 3 days, if the participant has passed day 10 of participation. If participants are able to tolerate the lower dose, they will continue participating in the trial albeit consuming the lower dose of the prebiotic treatment. Likewise, if a participant develops a condition that is an exclusion criterion or participant noncompliance increases risk of decreased study integrity, the participant will be withdrawn from the study.

If 5 of the first 20 subjects enrolled experience a change of 2 levels on questions 2, 6, 8, 16, 22, 26, 31, 33 on the PROMIS Gastrointestinal Symptom Scale (bloating, flatulence, watery stools, abdominal pain) compared to baseline or higher adverse event leading to subject discontinuation, we will stop the study temporarily and request the medical monitor to do an unblinded assessment of the data. The medical monitor (unblinded) will assess subjects who discontinued due to the specified adverse effects to determine if they are all in one arm of the study or range across arms. The medical monitor will assess if there is a safety signal in a specific arm or treatment dose over the other that warrants the closure of the study. Since the medical monitor will be the person determining continuation or discontinuation of the study, the study team will remain blinded and unbiased.

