10.2. Assessment of Safety

Participants will be withdrawn if during the first 10 days of study participation, they experience a 2 level change in one or more of the most reported side effects (bloating, flatulence, watery stools, abdominal pain as assessed by questions 2 (abdominal pain), 6 (abdominal discomfort), 8 (constipation), 16 (diarrhea), 22 (abdominal distention), 26 (abdominal bloating), 31 (nausea), or 33 (vomiting) on the PROMIS Gastrointestinal Symptom Scale as compared to their baseline responses. Participants who have surpassed 10 days of study participation and experience a 2 level change in one or more of the most reported side effects (as described above) as compared to baseline, they will be asked to reduce the dose of study product to one sachet of 7.5 mg per day. The study product can be taken all at once or distributed between two time points. If the PROMIS Gastrointestinal Symptom Scale does not improve upon reducing the dose, the participant will be withdrawn from the study. If 5 or more of the first 20 subjects enrolled experience a 2 level change in the most commonly reported side effects (bloating, flatulence, watery stools, abdominal pain) compared to baseline or higher adverse event leading to subject discontinuation, we will stop the study temporarily and request the medical monitor to do an unblinded assessment of the data. The medical monitor (unblinded) will assess subjects who discontinued due to the specified adverse effects to determine if they are all in one arm of the study or range across arms. The medical monitor will assess if there is a safety signal in a specific arm or treatment dose over the other that warrants the closure of the study. Since the medical monitor will be the person determining continuation or discontinuation of the study, the study team will remain blinded and unbiased.

Participants who choose to withdraw from the study will be followed up (via text or email communication) to determine safety and efficacy outcomes. Reasons for discontinuation will be documented in the study RedCap database.

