10.4. Safety Monitoring

Investigators will assess subjects at each visit and over the phone or via text (or email) each week of the study at days 0, 7±2, 14±2, 21±2, and 28±2 as well as day 7±2 post-intervention. If AEs as defined in this protocol are identified (a 2 level change in one or more of the symptoms as compared to baseline as assessed by questions 2 (abdominal pain), 6 (abdominal discomfort), 8 (constipation), 16 (diarrhea), 22 (abdominal distention), 26 (abdominal bloating), 31 (nausea), or 33 (vomiting) on the PROMIS

Gastrointestinal Symptom Scale). The treatment will be first be reduced to one 7.5g sachet per day (taken either at once or divided between two time periods if the participant has been participating for \geq 10 days. The treatment will be discontinued if the participant is in the first 10 days of participation, and the AE will be recorded. Also, participants who report severe side effects (interfering significantly with subject's usual function) will be withdrawn from the study immediately. If 5 or more of the first 20 subjects enrolled experience a 2 level change in the most reported side effects (bloating, flatulence, watery stools, abdominal pain as assessed by questions 2 (abdominal pain), 6 (abdominal discomfort), 8 (constipation), 16 (diarrhea), 22 (abdominal distention), 26 (abdominal bloating), 31 (nausea), or 33 (vomiting) on the PROMIS Gastrointestinal Symptom Scale compared to baseline or higher adverse event leading to subject discontinuation, we will stop the study temporarily and request the medical monitor to do an unblinded assessment of the data.

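### Section 9.6 assumes all missing data are completely at random, yet the protocol withdraws participants for GI symptoms; the population for symptom scores and the counting of stepped-down participants are not stated

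*Combined protocol and SAP*

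**What the plan says.** Section 9.6 expects 20% drop-out and states: "We assume the subjects will drop out randomly and all the missing data is missing completely at random (MCAR". It continues: "we will implement complete-case analysis for the primary statistical analysis". No aim is named and none is excepted. It then adds a check: "However, we will also explore the possibility that the missing data is not MCAR". The check compares drop-outs with non-drop-outs, and applies multiple imputation if the data are judged missing at random.

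Other sections make withdrawal a consequence of symptoms:

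- Section 6.7, for a two-level increase on any of eight PROMIS GI items: "withdrawn from the study if the participant is in the first 10 days of their participation".
- Section 10.2, same items: "Participants will be withdrawn if during the first 10 days of study participation, they experience a 2 level change". After a later dose reduction: "If the PROMIS Gastrointestinal Symptom Scale does not improve upon reducing the dose, the participant will be withdrawn from the study".
- Section 10.4, same trigger, but it stops treatment and does not mention withdrawal: "The treatment will be discontinued if the participant is in the first 10 days of participation, and the AE will be recorded". Participants with severe side effects "will be withdrawn from the study immediately".
- Sections 6.1 (Modification) and 10.1 also withdraw for severe side effects.

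Under Section 6.7, a participant who triggers after day 10 and tolerates a lower dose stays in the trial on that dose.

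The primary outcome in Section 4.4 is confirmation of 15 g/day as safe and tolerable on a GI symptom instrument. Section 9.2 reports the percentage with any AE on an intent-to-treat basis. Section 7.8 keeps some data from withdrawn participants for Objective 1 and none for Objective 2.

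**The concern.** Missing completely at random means that drop-out is unrelated to any data, observed or not. A rule that removes people because a recorded GI score rose is the opposite, and GI symptoms are what Aim 1 measures. If symptom scores are summarised in completers only, the summary leans towards people who tolerated the product.

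A related gap is not a missing-data problem. Participants stepped down after day 10 remain complete cases, but their later scores describe a lower dose. Participants withdrawn in the first 10 days were still on 10 g/day and never reached 15 g/day. The plan does not say how either group counts in a statement about 15 g/day. At stake is whether the trial's first objective can be answered from its own tables, and to whom the Aim 2 results apply.

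**Working it through.** **1. The plan's own figures.** Section 9.5 gives 60 recruited, 20% drop-out and 48 completers. 48 / (1 − 0.20) = 60 and 48 / 3 = 16, so these agree. Per arm that is 60 / 3 = 20 randomised and 20 − 16 = 4 drop-outs. Other sections give other sizes: 16 per group assigned (Sections 4 and 4.2), and 45 randomised, i.e. 15 per group (Section 8.6).

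**2. Is the trigger the primary outcome?** Sections 4.3 and 4.4 name the 38-point GSSC; the withdrawal rules name PROMIS. The Table of Events (7.1) labels Appendix 1 as PROMIS, and the list of appendices labels Appendix 1 as the GSSC. Section 8.1 measures tolerability side effects with PROMIS. I treat them as one instrument; the argument relies on that.

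**3. Which outputs are exposed?**

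| Output | Position |
|---|---|
| Percentage with any AE | Protected: intent to treat (9.2), and 10.4 treats the two-level change as an AE |
| Events over time, severity | Follows the intent-to-treat sentence in 9.2; most naturally the same population |
| Drop-out, adherence | Observed outcomes in their own right (4.3, 8.1) |
| Symptom-score summaries | No population stated; 9.6 is the only specific missing-data rule |
| Aim 2 markers | Sampled only at baseline and day 28 (4.3); withdrawn participants excluded (7.8) |

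Section 7.8 does not rescue the fourth row. The only visit it names is Visit 1, which is baseline, so read literally it keeps no on-treatment score. The Table of Events does schedule PROMIS and AE assessment at premature discontinuation, but no analysis says that this record is used.

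**4. Size.** The documents give no rate of symptom-triggered drop-out. Assume n = 20 per arm, of whom k of the 4 drop-outs are symptom-triggered at +2 levels on the same item at the last record. Everyone else has the completers' mean change c.

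All-randomised mean = ((20 − k)c + 2k) / 20

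| k | c = 0 | c = 0.25 |
|---|---|---|
| 0 | 0 | 0.25 |
| 1 | 0.1 | 0.34 |
| 2 | 0.2 | 0.43 |
| 3 | 0.3 | 0.51 |
| 4 | 0.4 | 0.60 |

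The completer-only mean is c in every row. For c = 0 and k = 4, the trigger may instead be spread evenly over the eight items, with no change on the others. The shift per item is then (4 × 2) / (8 × 20) = 0.05 levels.

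With 16 per arm and 3 drop-outs, the same-item maximum at c = 0 is 3 × 2 / 16 = 0.375. With 15 per arm and 3 drop-outs it is 3 × 2 / 15 = 0.40.

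**5. Precision of a direct count.** If symptom-triggered events were counted over all 20 randomised in an arm, exact 95% intervals would be 0/20 = 0% (0 to 16.8), 2/20 = 10% (1.2 to 31.7) and 4/20 = 20% (5.7 to 43.7).

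**The case against.** The plan has real safeguards. The intent-to-treat AE percentage keeps withdrawn participants. Drop-out and adherence are tolerability parameters, so a symptom-triggered withdrawal is itself an observed Aim 1 result. Sections 6.8 and 10.2 follow up people who choose to withdraw. Section 9(a) ties the handling of incomplete data to its documented causes. Section 9.6 itself allows for departures from its assumption. Aim 1 is descriptive, in a pilot whose tolerability sample size was not based on power.

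Most of this stands, and it rules out several stronger readings that a reader might infer:

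- *AE incidence is biased.* Not supported, given the intent-to-treat statement.
- *Tolerability is undefined.* Too strong. Sections 4.3 and 8.1 list components, and the synopsis and Section 9.2 gloss tolerability as absence of GI adverse effects. What is missing is a rule for counting dose-reduced and early-withdrawn participants.
- *By-week event summaries are completer-only.* The text does not say so.
- *Section 7.8 contradicts the imputation in 9.6.* The two can coexist: exclusion as the primary analysis, imputation as a conditional sensitivity analysis. One clarifying sentence would do.
- *A completer-only tolerability percentage will mislead.* No such percentage is planned.

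What survives is narrower. The check in 9.6 leaves the primary rule as it is, and does not say whether on-treatment symptom scores are among the clinical factors compared. By Section 9(a), a non-significant comparison is inconclusive, so it could not establish the assumption. No safeguard states a population for the symptom scores.

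**Conclusion.** The assumption in Section 9.6 is wrong as written, because Sections 6.1, 6.7, 10.1, 10.2 and 10.4 make part of the drop-out or treatment discontinuation depend on GI symptoms. That much follows from the text, given that the GSSC and PROMIS are one instrument.

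The consequence is limited to the symptom-score summaries, the reach of the Aim 2 results, and the unanswered question of who counts as tolerating 15 g/day. Under the stated assumptions with no mean change in completers, an item mean moves by between 0 and 0.4 levels. The upper end needs all four drop-outs in an arm to trigger on the same item. An even spread of four gives about 0.05 per item. These are illustrations, not estimates. The actual size is unknown, and so is the direction of any effect on the comparison with placebo, since drop-out may occur in any arm.

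This should be fixed before analysis; it does not threaten the AE table.

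**What to change.** 1. **Section 9.6.** Replace the completely-at-random premise. For Aim 1, analyse all randomised participants by arm, using every PROMIS and AE record up to and including the Premature Discontinuation assessment. Align Sections 7.8 and 9.6 with the intent-to-treat statement in 9.2, and use one name for the symptom instrument.
2. **Section 9.2, Aim 1.** Report per arm, with exact 95% confidence intervals, the number and percentage with symptom-triggered withdrawal, treatment discontinuation or dose reduction. Show those withdrawn before reaching 15 g/day separately. Do not present scores recorded after step-down as scores at 15 g/day.
3. **Aim 2.** Label complete-case results as applying to completers. Add a sentence saying that the exclusion in 7.8 defines the primary analysis and that imputation is a sensitivity analysis.

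Item 2 needs a single dose-reduction rule. Section 6.7 steps down to 5 g sachets twice daily; Section 10.2 to one sachet a day, printed as 7.5 mg; Section 10.4 to one 7.5 g sachet a day. For a trigger in the first 10 days, Sections 6.7 and 10.2 withdraw the participant, while 10.4 speaks of stopping treatment. These passages must be reconciled; no clinical rule is proposed here.

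The cost is SAP wording and a little extra analysis of data already scheduled, with no new visits, samples or participants. Reported tolerability may look less favourable.
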